4.5.8.5 Cannabis Withdrawal Scale (18 Years and Above)

The CWS is a 19-item scale with each item (withdrawal symptom) measured on a 0–10 numerical rating scale (NRS) (0 = Not at all; 5 = Moderately; 10 = Extremely). The patient or their caregiver is asked to record the extent to which each withdrawal symptom was experienced in the last 24 hours and also to rate the negative impact on normal daily activities (i.e., 2 separate scores are recorded for each item using the same 0–10 NRS). Scores are calculated as the sum of the 19 items for each measure, i.e. each separate score has a theoretical maximum of 190.

The CWS will be carried out for any patient completing the study or withdrawing early.

The 2 derived scores, recorded at each visit, will be summarized on a continuous scale. The change from core study baseline will also be included.

If any of the individual items are missing, for each measure, then the corresponding derived score will not be calculated.

The CWS was to be completed for patients aged 18 years and above only. However, summaries will be based on all patients who have a completed questionnaire, regardless of age.

4.5.8.6 Pediatric Cannabinoid Withdrawal Scale (4–17 Years)

The PCWS was developed from the 19-item validated CWS (adults) that assesses mood, behavioral and physical symptoms associated with cannabis, which was based on the Marijuana Withdrawal Checklist. The modified 10-item PCWS was developed from a low literacy version of the CWS. Symptoms specific to adult cannabis withdrawal have been removed and the wording has been amended to be comprehensible to children of the specified age range.

Ratings are based on a 4-point scale where 0 = none, 1 = a little bit, 2 = quite a bit, and 3 = a lot. This rating scale has been compacted from the original 11-point Likert scale used for the CWS in order to simplify the range of options to consider for potential intellectually disabled children. The PCWS was designed with epileptic children in mind as a tool to assess the safety of cannabinoid medications with respect to the stimulation of cannabinoid withdrawal syndrome when medications are withdrawn. As there may be a wide range of intellectual or developmental difficulties in severely epileptic children, from no intellectual or developmental impairment to extreme, the PCWS has been designed to be administered by a treating clinician, either directly to the child, or to the parent or caregiver of the child, reflecting on the child's symptoms within the chosen timeframe.

A derived score is calculated as the sum of the 10 items and has a theoretical maximum score of 30.

The PCWS will be carried out at the end of taper visit and at the safety phone call and follow-up visit for any patient completing the study or withdrawing early.

The derived score recorded at each visit will be summarized on a continuous scale by visit. The change from baseline will also be included.

If any of the individual items are missing, then the derived score will not be calculated.

The PCWS was to be completed for patients aged 4 to 17 years only. However, summaries will be based on all patients who have a completed questionnaire, regardless of age.

4.5.8.7 Subject/Caregiver Global Impression of Change

The SGIC and CGIC comprise the following questions to be rated on a 7-point scale:

CGIC:

- Since your child started treatment, please assess the status of your child's overall condition (comparing their condition now to their condition before treatment) using the scale below.

SGIC:

- Since you started treatment, please assess the status of your overall condition (comparing your condition now to your condition before treatment) using the scale below.

The possible responses are: Very Much Improved; Much Improved; Slightly Improved; No Change; Slightly Worse; Much Worse; Very Much Worse.

Each response will be coded with a score from 1 to 7, where 1 = Very Much Improved, and 7 = Very Much Worse.

The SGIC and CGIC response/score, recorded at each visit, will be summarized separately, on both a categorical and continuous scale, by treatment group.

A combined score will also be summarized and will be defined as follows:

- If both a CGIC and SGIC are completed then the CGIC will be used.
- If only a CGIC is completed then the CGIC will be used.
- If only a SGIC is completed then the SGIC will be used.

4.5.8.8 Subject/Caregiver Global Impression of Change in Seizure Duration

The SGICSD and CGICSD comprise the following questions to be rated on a 3-point scale for each seizure type:

CGICSD:

- Since the patient started treatment, please assess the average duration of the patient's seizures (comparing their condition now to their condition before treatment) using the scale below.

SGICSD:

- Since you started treatment, please assess the average duration of your seizures (comparing your condition now to your condition before treatment) using the scale below.

The 3 possible responses are:

- Decrease in average duration.
- No change in average duration.
- Increase in average duration.

The patient/caregiver will be asked to assess the average duration of seizures at Visit 1 (prior to commencement of IMP) as a memory aid for assessment at the end of treatment visit.

Each response will be coded with a score from 1 to 3, where 1 = Decrease in average duration, and 3 = Increase in average duration.

For each seizure type, the SGICSD and CGICSD will be summarized separately for each visit.

A combined score will also be summarized. The combined score will be defined as follows:

- If both a CGICSD and SGICSD are completed then the CGICSD will be used.
- If only a CGICSD is completed then the CGICSD will be used.
- If only a SGICSD is completed then the SGICSD will be used.

4.5.8.9 Inpatient Hospitalizations due to Epilepsy

The number of patients with any inpatient epilepsy-related hospitalizations since the previous visit will be presented for each relevant visit, including the baseline visit as established in the core studies.

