9.2.2 Visit 2 (Day 15)

Visit 2 will take place 14 days after Visit 1. A visit window of ± 3 days from the scheduled visit date is permitted, but it is preferred that the visit is performed on the scheduled visit day where possible.

The following assessments will be made at Visit 2: vital signs, physical examination (including height and body weight) and ECG. Clinical laboratory samples (blood and urine [where possible]) will be taken for hematology, biochemistry and urinalysis. The patient's IVRS report and paper diary will be reviewed and the information recorded along with information regarding AEs, IMP, epilepsy-related hospitalizations, concomitant medications and/or changes to medication. The Investigator must assess adherence to the titration regimen.

All IMP (used and unused) will be collected and a check of the returned IMP against usage should be made. Patients/caregivers will then receive a 2-week supply of IMP.

During titration of doses above 20 mg/kg/day, safety telephone calls must be made every 7 days (± 3 days) until stable dosing is achieved. During these calls, caregivers will be asked for information on AEs, epilepsy-related hospitalizations, concomitant medications and/or changes to medication.

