9.2.7 Visit 8 (76 weeks)

Visit 8 will take place 28 weeks after Visit 7 (76 weeks after Visit 1). A visit window of ± 7 days from the scheduled visit date is permitted, but it is preferred that the visit is performed on the scheduled visit day where possible.

The following assessments will be made: vital signs, physical examination (including height and body weight), ECG, C-SSRS, Vineland-II, QOLCE/QOLIE, S/CGIC and S/CGICSD. Clinical laboratory samples (urine [where possible] and blood) will be taken for hematology, biochemistry and urinalysis. The patient's IVRS report and paper diary will be reviewed and the information recorded along with information regarding AEs, IMP, epilepsy-related hospitalizations, concomitant medications and/or changes to medication. The Investigator must assess adherence to the dosing regimen.

A 14-week supply of IMP will be issued to the patient/caregiver.

Following Visit 8, safety telephone calls must be made every 4 weeks (± 7 days) to assess AEs, epilepsy-related hospitalizations, concomitant medications and/or changes to medication. In addition, during titration of doses above 20 mg/kg/day, safety telephone calls must be made every 7 days (± 3 days) until stable dosing is achieved.

At least 1 dispensing appointment will be scheduled to occur between Visit 8 and Visit 9. The dispensing appointment date(s) will be calculated from Visit 8. At each dispensing appointment caregivers will be dispensed with sufficient IMP to be administered until the next scheduled appointment. Patients need not attend the dispensing appointments.

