9.2.11 Visit 12 (184 weeks)

Visit 12 will take place 28 weeks after Visit 11 (184 weeks after Visit 1). A visit window of ± 7 days from the scheduled visit date is permitted, but it is preferred that the visit is performed on the scheduled visit day where possible.

The following assessments will be made: vital signs, physical examination (including height and body weight), ECG, C-SSRS, Vineland-II, QOLCE/QOLIE, S/CGIC and S/CGICSD. Clinical laboratory samples (urine [where possible] and blood) will be taken for hematology, biochemistry and urinalysis. The patient's IVRS report and paper diary will be reviewed and the information recorded along with information regarding AEs, IMP, epilepsy-related hospitalizations, concomitant medications and/or changes to medication. The Investigator must assess adherence to the dosing regimen.

A 14-week supply of IMP will be issued to the patient/caregiver.

Following Visit 12, safety telephone calls must be made every 4 weeks (± 7 days) to assess AEs, epilepsy-related hospitalizations, concomitant medications and/or changes to medication. In addition, during titration of doses above 20 mg/kg/day, safety telephone calls must be made every 7 days (± 3 days) until stable dosing is achieved.

At least 1 dispensing appointment will be scheduled to occur between Visit 12 and 'End of Treatment' visit. The dispensing appointment date(s) will be calculated from Visit 12. At each dispensing appointment caregivers will be dispensed with sufficient IMP to be administered until the next scheduled appointment. Patients need not attend the dispensing appointments.

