9.2.16 Safety Telephone Calls

From Visit 3 until the 'End of Treatment' visit, safety telephone calls must be made every 4 weeks (\pm 7 days). In addition, during titration of doses above 20 mg/kg/day, safety telephone calls must be made every 7 days (\pm 3 days) until stable dosing is

achieved. All safety telephone calls will assess AEs, epilepsy-related hospitalizations, concomitant medications and/or changes to medication.

A post-taper safety telephone call must also be made (see [Section 9.2.14](#)).

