3.3.2 Secondary Endpoints

All Patients:

- Change in quality of life as measured with Quality of Life in Childhood Epilepsy (QOLCE) if 18 years of age or younger, or Quality of Life in Epilepsy (QOLIE) if 19 years of age or older, relative to the pre-randomization baseline of the Core Study, if assessed during the Core Study.
- Change in Subject/Caregiver Global Impression of Change (S/CGIC), relative to the pre-randomization baseline of the Core Study.
- Change in adaptive behavior as measured with the Vineland Adaptive Behavior Scales, Second Edition (Vineland-II), relative to the pre-randomization baseline of the Core Study, if assessed during the Core Study.
- Change in the number of inpatient epilepsy-related hospitalizations (number of hospitalizations due to epilepsy in each 28-day period), relative to the pre-randomization baseline of the Core Study.
- Change in the use of rescue medication (number of days used in each 28-day period), relative to the pre-randomization baseline of the Core Study.
- Maintenance of seizure frequency reduction and freedom from seizures during the OLE study.
- Percentage change in the frequency of total seizures, relative to the pre-randomization baseline of the Core Study.
- Number of patients considered treatment responders, defined as those with a $\geq 25\%$, $\geq 50\%$, $\geq 75\%$, or 100% reduction in total seizures, relative to the pre-randomization baseline of the Core Study.
- Number of patients experiencing a $> 25\%$ worsening, $- 25$ to $+ 25\%$ no change, 25 – 50% improvement, 50 – 75% improvement or $> 75\%$ improvement in total seizures, relative to the pre-randomization baseline of the Core Study.
- Percentage change in the frequencies of subtypes of seizures, relative to the pre-randomization baseline of the Core Study.
- Changes in duration of seizure subtypes as assessed by the Subject/Caregiver Global Impression of Change in Seizure Duration (S/CGICSD), relative to the pre-randomization baseline of the Core Study.
- Change in the number of episodes of status epilepticus, relative to the pre-randomization baseline of the Core Study.
- Change in cognitive function as measured with a cognitive assessment battery, relative to the pre-randomization baseline of the Core Study, if assessed during the Core Study.

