4. STATISTICAL METHODS

4.1 General Considerations

All tables will be presented by indication (where appropriate), including an overall count, as follows:

Dravet Syndrome (N=XX)	Lennox-Gastaut Syndrome (N=XX)	Overall (N=XX)
------------------------	--------------------------------	----------------

In all tables, listings and figures, the study visits will be referred to and labelled as per [Table 2](#)

Table 2 Study Visits

Actual Visit	Visit Label
Visit 1: Day 1	Day 1
Visit 2: Day 15	Day 15
Visit 3: Day 29	Day 29
Visit 4: Day 85	Day 85
Visit 5: Month 6 or Week 24	Week 24
Visit 6: Month 9 or Week 38	Week 38
Visit 7: Week 48 or End of Treatment (only patients who completed at 1 year)*	Week 48
Visit 8: Week 76	Week 76
End of Treatment (only patients who completed on or after Day 400)*	End of Treatment

End of Treatment (withdrawn patients only)	End of Treatment
End of Taper	End of Taper
Post-Taper Safety Call	Post-Taper Safety Call
Safety Follow-Up	Safety Follow-Up

* For some patients, the end of treatment visit occurs after one year in the OLE, whereas for other patients the end of treatment visit occurs after two or more years in the OLE.

Unless stated otherwise, continuous variables will be summarized showing the number of non-missing values (n), mean, standard deviation, median, minimum and maximum and categorical variables will be summarized showing the number and percentage of patients falling in each category. For continuous summaries of seizure frequency, the lower and upper quartiles will also be presented.

Minimum and maximum values will be presented to the same decimal precision as the raw data. Mean and median will be presented to one more decimal place than the raw data, and standard deviation to 2 more decimal places than the raw data. Percentages will be presented to one decimal place.

For patients who enter the OLE on the same day as the core study end of treatment or end of taper visit, the CRF for this study did not require some data to be entered for a second time. Hence, for visit based endpoints, if a patient does not have data entered in this study at Visit 1, then data from the end of treatment or end of taper visit in the core study will be used, provided that the date of collection is on Day 1 of the OLE.

Unless otherwise stated, all summaries will be presented by indication.

All analyses and summaries will be produced using SAS Version 9.4.

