4.7 Changes in the Conduct of the Study or Planned Analysis

A number of additional summaries have been added, compared to the protocol, and are described in the sections above. These additions are not detailed in this section.

The following endpoints described in the protocol are not included as part of the planned analysis in this SAP due to the nature of the collection of data for the endpoint not being compatible with a continuous summary of change from baseline:

- Change in the number of inpatient epilepsy-related hospitalizations (number of hospitalizations due to epilepsy in each 28-day period), relative to the pre randomization baseline of the Core Study.
- Change in the use of rescue medication (number of days used in each 28 day period), relative to the pre-randomization baseline of the Core Study.
- Change in the number of episodes of status epilepticus, relative to the pre randomization baseline of the Core Study.

The following endpoints described in the protocol are not included as part of the planned analysis in this SAP as they were not deemed necessary for the assessment of the objectives of this trial:

- Number of patients experiencing a > 25% worsening, – 25 to + 25% no change, 25–50% improvement, 50–75% improvement or > 75% improvement in total seizures, relative to the pre-randomization baseline of the Core Study.
- Percentage change in the frequencies of subtypes of seizures, relative to the pre-randomization baseline of the Core Study.
- Percentage change in total non-convulsive seizure frequency, relative to the pre-randomization baseline of the Core Study.
- Number of patients experiencing a > 25% worsening, – 25 to + 25% no change, 25–50% improvement, 50–75% improvement or > 75% improvement in convulsive seizures, relative to the pre-randomization baseline of the Core Study.
- Percentage change in the number of non-drop seizures, relative to the pre-randomization baseline of the Core Study.
- Number of patients experiencing a > 25% worsening, – 25 to + 25% no change, 25–50% improvement, 50–75% improvement or > 75% improvement in drop seizures, relative to the pre-randomization baseline of the Core Study.

In addition, the protocol included summaries of medical history. However, this was not collected as part of the OLE and is reported as part of the core studies only.

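### Table 14.3 counts patients hospitalized since the previous visit with no adjustment for unequal gaps, and SAP 4.7 leaves seizure frequencies listed as objectives in SAP 2.2 without a table

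*SAP*

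**What the plan says.** **Hospitalizations.** SAP 3.3.2, like protocol 4.1.2, defines the endpoint as a change from core-study baseline in the "number of hospitalizations due to epilepsy in each 28-day period". SAP 4.7 withdraws that analysis "due to the nature of the collection of data for the endpoint not being compatible with a continuous summary of change from baseline". What remains is SAP 4.5.8.9, tabulated as Table 14.3: "The number of patients with any inpatient epilepsy-related hospitalizations since the previous visit will be presented for each relevant visit", with the core-study baseline visit alongside. No rate, person-time denominator or common window is given.

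The protocol schedule is uneven. At one end, "Visit 2 will take place 14 days after Visit 1" (9.2.2). At the other, "Visit 8 will take place 28 weeks after Visit 7" (9.2.7). Hospitalizations are also asked about between clinic visits: "All safety telephone calls will assess AEs, epilepsy-related hospitalizations, concomitant medications and/or changes to medication" (9.2.16), every 4 weeks from Visit 3. SAP 4.5.8.9 does not mention these calls.

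On labels, SAP 4.1 says: "In all tables, listings and figures, the study visits will be referred to and labelled as per" its Table 2. That table has no label for Visits 9 to 12 or for the routine calls. It uses one End of Treatment label for withdrawn patients and for completers from Day 400 on.

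**Seizure frequencies.** SAP 2.2 lists as secondary objectives the frequency of seizure subtypes (with total seizures), of non-convulsive seizures in DS and of non-drop seizures in LGS. SAP 4.7 removes the matching endpoints on the ground that the trial's objectives do not require them. SAP 4.5.9 and the list of tables provide frequency tables only for total, drop and convulsive seizures.

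**The concern.** The chance that a patient has at least one admission grows with the time over which admissions are counted. A table whose rows cover 2 weeks in one place and 28 weeks in another therefore shows different percentages even when risk is constant. The gaps lengthen as the study goes on, so the artefact would look like worsening with time on treatment and could mask a real reduction.

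Table 14.3 is the only table dedicated to the objective on need for epilepsy hospitalization. With no hypothesis testing planned, the printed rows are the result.

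The seizure-frequency part is a contradiction within the SAP. Two listed objectives (non-convulsive in DS, non-drop in LGS) and the subtype half of a third would be reported with no table, for a reason that SAP 2.2 contradicts.

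**Working it through.** **1. Gaps.** The scheduled weeks in protocol 9.2.1 to 9.2.12 are 0, 2, 4, 12, 24, 36, 48, 76, 104, 132, 156, 184 and 208 (maximum end of treatment). Successive differences are 2, 2, 8, 12, 12, 12, 28, 28, 28, 24, 28 and 24 weeks. The first eleven match the intervals the protocol states; the last is 208 − 184 = 24.

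**2. Expected row values if visit means clinic visit.** The documents give no hospitalization rate, so r (per 28 days) is assumed and held constant. For a gap of w weeks, P(at least one) = 1 − exp(−r × w/4). For example, at r = 0.05 and w = 28: 1 − exp(−0.35) = 29.5%.

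| Gap (weeks) | r = 0.02 | r = 0.05 | r = 0.10 |
|---|---|---|---|
| 2 | 1.0% | 2.5% | 4.9% |
| 8 | 3.9% | 9.5% | 18.1% |
| 12 | 5.8% | 13.9% | 25.9% |
| 24 | 11.3% | 25.9% | 45.1% |
| 28 | 13.1% | 29.5% | 50.3% |

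At r = 0.05 the 28-week row is about 12 times the 2-week row.

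**3. Patients who differ in risk.** With gamma frailty of shape k, P = 1 − (1 + r × w/(4k))^(−k). At r = 0.05, k = 0.25 gives 2.4% at 2 weeks and 19.7% at 28 weeks (8.3-fold); k = 0.1 gives 2.2% and 14.0% (6.3-fold). The artefact shrinks but remains.

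**4. Can it hide a benefit?** Halving the rate makes 28 weeks equivalent to 14 weeks at the full rate, which is more than 12. At r = 0.05 the halved 28-week row is 1 − exp(−0.025 × 7) = 16.1%, above the unhalved 12-week row of 13.9%. With frailty the pairs are 12.4% against 11.1% (k = 0.25) and 9.6% against 8.8% (k = 0.1).

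**5. If the calls count as visits.** Each row from Day 85 on then covers about the last 4 weeks, so those rows are comparable. Routine calls have no label in Table 2, so the remainder of each gap, (w − 4)/w, is not shown: 4 of 8 weeks (50%), 8 of 12 (67%), 24 of 28 (86%).

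**6. End of Treatment row (clinic-visit reading).** A completer on Day 400 last seen at Week 48 (Day 337) contributes 63 days, or 9 weeks: 10.6% at r = 0.05. A Week 208 completer last seen at Visit 12 contributes 24 weeks: 25.9%. Withdrawn patients contribute whatever time has passed since their last visit. One row pools all of these.

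**7. Seizure frequencies, side by side.**

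| Listed in SAP 2.2 | Status in SAP 4.7 | Table planned |
|---|---|---|
| Non-convulsive frequency (DS) | dropped | none |
| Non-drop frequency (LGS) | dropped | none |
| Total and subtype frequency (all) | subtype part dropped | total only: 9.1.1.1, 9.1.1.2, 9.7.1, 9.7.2 |

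The data are collected: SAP 4.5.9 says subtype frequencies are reported to the IVRS every 7 days. SAP 4.1.4.4 defines total as convulsive plus non-convulsive, and SAP 4.1.4.5 takes drop seizures from the IVRS, so both missing groups can be obtained by subtraction.

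**The case against.** The strongest reply is that both departures are openly declared in SAP 4.7, that the study is single-arm and descriptive, and that the SAP authors worked from the CRF and cite how the data were collected. Disclosure is granted; nothing is hidden. But the stated reason concerns a continuous change from baseline. It explains dropping a per-patient change score, not replacing it with counts over unequal intervals. A pooled rate needs no change score, though it does need counts. Protocol 9.1.4 says the number of admissions is recorded, but the CRF was not available here, so a data limit cannot be excluded. The fix therefore carries a fallback.

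Rows with equal scheduled gaps do compare fairly (Visits 5 to 7; Visits 8 to 10), and this stands. So does the point that these admissions are also captured as serious adverse events: Tables 12.1 and 12.2 and Listing 12 include them, and Listing 9.5 gives patient-level data. None of these tables isolates epilepsy admissions.

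Three stronger readings are tempting and not supported:
- A reader might infer that Table 14.3 will certainly show a spurious rise. That holds only if a visit means a clinic visit, which the SAP does not settle.
- A reader might infer from the missing labels for Visits 9 to 12 that the End of Treatment row looks back to Week 76. The protocol records hospitalizations at those visits, and the rule looks back to the previous visit, not to the previous label.
- A reader might take Table 2's label for Visit 6, which differs from the protocol's Week 36, as altering the gaps on either side. A label does not change when patients attended.

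**Conclusion.** The point holds in conditional form. As written, SAP 4.5.8.9 gives either rows that differ through interval length alone (clinic-visit reading) or rows that omit half or more of every gap of 8 weeks or longer (calls counted). These harms are alternatives; both cannot occur, and each needs a change of wording. On the first reading the size is 2.5% to 29.5% at an assumed 0.05 per 28 days, with 1.0% to 13.1% at 0.02 and 4.9% to 50.3% at 0.10. This rests on a constant rate, independent events and attendance on schedule; frailty lowers the fold-difference from about 12 to between 6 and 8. No numerical comparison with baseline is relied on, because the look-back of the baseline row is not stated.

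The contradiction between SAP 4.7 and SAP 2.2 needs no assumption. Both matters concern secondary, descriptive output. They should be fixed before the tables are produced, but they do not touch the primary safety endpoint.

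**What to change.** **Hospitalizations (SAP 4.5.8.9, Table 14.3).**
- Define the previous visit and state whether the 4-weekly calls count.
- Keep the patient count and add, per row, total hospitalizations ÷ total patient-days × 28. Put the baseline on the same scale where its look-back is known.
- If the CRF holds only yes/no data, print patient-days and median interval length per row instead.
- Include rows for Visits 9 to 12, and show withdrawn patients separately from completers at End of Treatment.

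The cost is SAP wording and one revised table. The drawback is that a few patients with many admissions can drive a pooled rate, which is why the patient count should stay beside it.

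**Seizure frequencies (SAP 4.5.9, 4.7).**
- Add descriptive frequency and percentage-change tables for non-convulsive seizures in DS (total minus convulsive) and non-drop seizures in LGS (total minus drop), plus a subtype frequency table, from the weekly IVRS data.
- Limit percentage change to patients with a non-zero baseline for that type and print the number excluded.
- Failing that, amend SAP 2.2 and 3.3.2 with a specific reason.

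The cost is three tables and no new data. The subtype table is long: the protocol's Definition of Terms lists eight subtypes, and 208 ÷ 12 gives about 17 twelve-week periods. Exempting these tables from the LOCF repeat, or adding a row for worsening above 25%, is a matter of preference and not part of the correction.
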